A. Background: Optic nerve (ON) originates from eyeball and terminates in the brain. It has intraconal course, extraconal course and intracranial course. Extraconal course of optic nerve shows variations in population. Relationship of optic nerve with posterior paranasal sinus (ethmoid and sphenoid sinuses) are of great clinical importance. Most commonly, ON is supero-lateral to the sphenoid sinus. However, varied protrusion of ON into the posterior paranasal sinuses are seen. Most important of them is onodi cells. If the optic nerve lies just lateral to posterior ethmoid cells, the ethmoid cell is called onodi cell. During endoscopic sinus surgery (ESS), there is high chance of injury to optic nerve if there is optic nerve. According to DeLano classification, there are four types of optic nerve course. Type -I: optic nerve is supero-lateral to sphenoid sinus, Type 2: ON courses superior to sphenoid sinus with less than 50% indentation in coronal section, Type 3: ON courses superior to sphenoid sinus with more than 50% indentation in coronal section. Type 4: ON is just lateral to ethmoid and sphenoid sinuses (i.e., Onodi cell). While coursing posterior paranasal sinuses, the optic nerves show dehiscence. The optic nerve is encased by dura and thin periosteum. The periosteum might not be present in all cases and while coursing through the sinuses, they are exposed open. These kinds of optic nerves are prone to injury during ESS. Thus, it is imperative to know prevalence of different types of course of optic nerve and dehiscence of optic nerve while coursing through posterior paranasal sinuses.

B. Rationale of Study/ Justification:

The variants of optic nerve course in relation to posterior paranasal sinuses are of clinical importance since some of the variants are prone to injury of optic nerve during functional endoscopic sinus surgery. Prior knowledge of course of optic nerve is of utmost importance

in order to prevent injury of optic nerves. However, there is lack of such kind of study in Nepal. Thus, it is imperative to know true prevalence of different anatomical variants of optic nerve course.

C. Objectives of the study:

General objective: To describe different course of optic nerve in relation to posterior paranasal sinuses and optic nerve dehiscence in MDCT.

Specific objective:

- To obtain the prevalence of different types of course of optic nerves according to DeLano classification in the MDCT of patients visiting our hospital. According to DeLano classification, there are four types of optic nerve course. Type -1: optic nerve is supero-lateral to sphenoid sinus, Type 2: ON courses superior to sphenoid sinus with less than 50% indentation in coronal section, Type 3: ON courses superior to sphenoid sinus with more than 50% indentation in coronal section. Type 4: ON is just lateral to ethmoid and sphenoid sinuses (i.e., Onodi cell).
- To obtain prevalence of optic nerve dehiscence in the MDCT of patients visiting our hospital.
- To obtain prevalence of pneumatized anterior clinoid process in the MDCT of patients visiting our hospital.

3. Literature Review with References (relevant up to five)

In a study by Itagi et al(1), in Indian ethnics, 200 optic nerve canals were assessed and grouped into four types based on the modification of Delano et al. classification. The most common optic nerve course (ONC) was Type-1 (60%), followed by Type-2 (15%), Type-3 (14%) and Type-4 (11%). Dehiscence was seen in 35(17.5%) mostly in Type-3 canals. Pneumatized anterior clinoid process (PACP) was seen in 30 (15%). In another study by BN Ravindra et al(2), in population of

Karnataka, Type 1, Type 2, Type 3, and Type 4 optic nerves was present in 83.33%, 8.87%, 12.1%, and 21.78% respectively. Bilateral Type 1 optic nerves was present in 58.88% patients, both Type 2 and Type 3 optic nerves were seen bilaterally in 3.23% of patients and bilateral Type 4 optic nerve was seen in 10 (8.06%) cases. Optic nerve Type 1 (83.88%) was the most frequent nerve type, followed by Type 4 (21.78%). In another study done by Braggs et al(3) in south Indian population, type 1 had a prevalence of 61.8%, type 2 had a prevalence of 17.8%, type 3 had a prevalence of 7.6%, type 4 had a prevalence of 12.8%. In another study done by Lakhani Mubina et al(4) type 1 ON was found to be the most frequent type; 55.93%, followed by type 2 with a frequency of 26.85%. However, type 3 and type 4 appeared less frequently, that is 11.1% and 6.11%, respectively. When comparing right and left sides it was noted that the frequency of type 1 optic nerve was found to be higher on both right and left sides with a value of 56.30% and 55.5%, respectively. Type 2 showed a frequency of 26.67% on right side and 27% on left side. Type 3 was identified to be 11.4% and 10.7% on right and left sides, respectively. Type 4 optic nerve was found to be the least common type in our study on both sides, i.e., 5.56% on the right side and 6.67% on the left side.

Bibliography

2. Bn R, C D. Evaluation of optic nerve variations in relation to posterior paranasal sinuses among study population of Mandya District of Karnataka State. *Int J Radiol Diagn Imaging*. 2020 Jul 1;3(3):16–20.
3. Braggs A, S KK. CT Study of Relationship of Optic Nerve to Posterior Paranasal Sinuses. *Int J Contemp Med Surg Radiol [Internet]*. 2018 Dec [cited 2023 Jun 27];3(4). Available from: https://www.ijcmsr.com/uploads/1/0/2/7/102704056/ijcmsr_161.pdf
4. Mubina Lakhani, Muhammad Ali, Madeeha Sadiq. Analysis of Optic Nerve Types in Relation to Posterior Paranasal Sinuses: A Computed Tomographic (CT) Study. *Ann ABBASI SHAHEED Hosp KARACHI Med Dent Coll*. 2017 Dec 31;22(4):249–54.

4. Research Methodology:

- A. Study type: Quantitative Study
- B. Study design: Retrospective Cross Sectional Observational Descriptive Study
- C. Sample size: Minimum 319 patient's CT scan; The size was calculated by the following formula for sample size:

$$n = Z^2 P (1-P) / d^2 , \text{ Where:}$$

Z- 2.576 (for 99 percent confidence interval)

P- Prevalence of most common anatomical variant from previous study (60 %)

d- margin of error (5%).

Calculation: $(2.576 \times 2.576 \times 0.6 \times 0.4) / (0.05 \times 0.05) = 637$ optic nerve canals

(Since 1 patient has 2 optic nerve canals, number of CT to be studied =319)

- D. Inclusion and Exclusion Criteria: All MDCT scan of PNS referred for evaluation of chronic rhinosinusitis and nasal polyposis and Head referred for evaluation of headache, dizziness, loss of consciousness in patients >13 years age are included in the study. MDCT PNS and head done for evaluation of trauma and tumors are excluded from the study.
- E. Data collection methods/tools: Images will be studied and findings will be recorded in predesigned Proforma. The proforma is attached herewith.
- F. Data analysis methods/tools: Prevalence of the variations of optic nerve course was calculated by using previous study in Indian population and free software like epi info.

5. Work plan/GANTT chart (start, progression, completion time for study/research) and Budgeting.

GIH-IRC Research Proposal Approval Format- Form A

S N	Tasks	From	To	August	September	October	November
1	Extraction of data	1 August	31 August				
2	Study of data and categorization	1 September	30 September				
3	Data analysis and obtaining result	1 October	31 October				
4	Preparing Manuscript	1 November	30 November				

Total duration of study will be of 4 months after the approval.

Funds will be generated from the involved investigators.

First month- Extraction of data from August 1 to August 31 2023

Second month- Study of the data collected and categorized accordingly.

Third month- Data analysis and obtaining the results

Fourth month- Preparing Manuscript.

BUDGET

ITEMS	Unit	Price per unit	APPROXIMATE COST
Stationary			Rs. 1000

GIH-IRC Research Proposal Approval Format- Form A

Statistician			Rs. 5000
Miscellaneous			Rs. 5000
TOTAL			Rs. 11000

Declaration (Please tick)

S.no	Title	Yes	No
1.	Are foreign researcher / institutions involved in the research?		No
2.	Is your research being funded by organization or agency?		No
3.	Are vulnerable members of the population required for this research? (Except routine work treatment/observation in hospital set up e.g., pediatric, obstetric patient, patient in psychiatric hospital, etc.)		No
4.	Are there significant risks involved for the participants?		No

If any of the declaration is "yes" then please fill up the form "B" with supplemental detail information.

Declaration by the principal investigator

I hereby certify that the above-mentioned statements are true. I have read and understood the regulation of the Nepal Health Research Council (NHRC) and will act accordingly.

[figure not shown]
If the research is terminated, for any reason, I will notify IRC-GIH of this decision and provide the reasons for such actions. I will provide a written notice upon the completion of the research

GIH-IRC Research Proposal Approval Format- Form A

as well as a final summary/full report of the research study. For publication in a journal, I shall acknowledge the IRC-GIH approval and shall provide the committee copy of such publication.

Full name (*first/middle/last*): [name]

(Signature)

Date: 10/07/2023

Email: [contact]

Contact No: (*preferably mobile no*) : [name]

Data Collecting Instrument of the study ‘EVALUATION OF VARIATIONS OF OPTIC NERVE COURSE IN RELATION TO POSTERIOR PARANASAL SINUSES IN MDCT IN A TERTIARY CARE CENTER OF NEPAL’

Name:

Age:

Sex:

Date:

1)Course of optic nerve: Right:

Left:

2)Wall dehiscence of ON: Right side (Present, absent); Left side (Present, absent)

3)Pneumatization of anterior clinoid process: Right side (Present, absent); Left side (Present, absent)

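### Do the differing Onodi and Type 4 wordings leave the Type 4 prevalence undefined?

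*Protocol*

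**What the plan says.** The first specific objective (Protocol, C. Objectives of the study) is the prevalence of the four DeLano types of optic nerve course. Type 1 reads "Type -1: optic nerve is supero-lateral to sphenoid sinus". Types 2 and 3 place the nerve above the sphenoid sinus and differ by the degree of indentation, for example "Type 3: ON courses superior to sphenoid sinus with more than 50% indentation in coronal section". Type 4 reads "Type 4: ON is just lateral to ethmoid and sphenoid sinuses (i.e., Onodi cell"). The Type 4 sentence in A. Background is the same.

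A. Background also contains a separate sentence on the Onodi cell: "If the optic nerve lies just lateral to posterior ethmoid cells, the ethmoid cell is called onodi cell". Of the ways the nerve can protrude into the posterior sinuses, it says "Most important of them is onodi cells".

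The Data Collecting Instrument has an open entry for each side, beginning "1)Course of optic nerve: Right". The next item has coded answers: "2)Wall dehiscence of ON: Right side (Present, absent); Left side (Present, absent").

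**The concern.** Three features of the text invite doubt.

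- **Two wordings.** The Onodi sentence needs contact with the posterior ethmoid only, while the Type 4 sentence names the ethmoid and the sphenoid. Read word for word, a nerve beside a posterior ethmoid cell alone has an Onodi cell but no type.
- **No stated exclusivity.** Types 1 to 3 are described by the sphenoid relation and say nothing about the ethmoid. A nerve that is supero-lateral to the sphenoid in one section and beside a posterior ethmoid cell in another could satisfy two descriptions. An indentation of exactly 50% satisfies neither Type 2 nor Type 3.
- **An open entry.** The form gives no type codes for the nerve course, so the recorded data might not show which reading was used.

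Type 4 is uncommon in the cited per-nerve figures, and the Protocol treats the Onodi cell as the variant that matters most. If readers split on the wording, the estimate would shift, and a larger sample would not correct it.

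**Working it through.** **1. The wordings side by side.** The Onodi sentence says when an ethmoid cell earns that name. The Type 4 sentence classifies a nerve and states in brackets that this is the Onodi configuration. Taking possible nerves in turn:

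| Nerve lies beside | Type 4 sentence, word for word | Type 4 sentence with its gloss |
|---|---|---|
| posterior ethmoid and sphenoid | Type 4 | Type 4 |
| posterior ethmoid only | no type | Type 4 |
| posterior ethmoid, and also fits Type 1, 2 or 3 at another level | Type 1, 2 or 3 | Type 4 is the natural choice, though no tie-break is written |

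The readings part only if the gloss is ignored. The last row is a hypothetical case; the documents do not say that such nerves occur.

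**2. Is one type per nerve intended?** The form has one entry per side. The type percentages quoted in the Literature Review add up as follows:

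- first study: 60 + 15 + 14 + 11 = 100
- third study: 61.8 + 17.8 + 7.6 + 12.8 = 100.0
- fourth study: 55.93 + 26.85 + 11.1 + 6.11 = 99.99
- second study: 83.33 + 8.87 + 12.1 + 21.78 = 126.08

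The second total looks like overlapping types, but it fits a count of patients with the type on at least one side. Ten bilateral Type 4 cases at 8.06% imply 10/0.0806 = 124 patients. The Protocol gives Type 1 in this study as both 83.33% and 83.88%; 104/124 = 83.87% fits the latter. Patients with each type are then about 104, 11, 15 and 27, total 157. Bilateral cases, reading 3.23% as applying to Type 2 and to Type 3 separately, are about 73, 4, 4 and 10, total 91. Nerves equal patients with the type plus bilateral cases: 157 + 91 = 248 = 2 × 124. So every nerve has one type there too.

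**3. Scale.** The planned size reproduces: 2.576² × 0.6 × 0.4 / 0.05² = 637.03 canals, and 637.03/2 = 318.5, rounded up to 319 scans (638 nerves). It uses Type 1 only.

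- Cited per-nerve Type 4 figures of 6.11%, 11% and 12.8% correspond to about 39, 70 and 82 of 638 nerves.
- One percentage point is 638/100 = 6.4 nerves.
- At 11%, taking nerves as independent, the 99% half-width is 2.576 × √(0.11 × 0.89/638) = 3.2 points, or 20.4 nerves.
- The Protocol's stated margin of 5 points, set for Type 1, is 0.05 × 638 = 31.9, so 32 nerves. That is 32/70 = 46% of the expected Type 4 nerves moving out, or 32/568 = 5.6% of the rest moving in.

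These counts show what a shift of a given size would take. They do not estimate a shift, because no document reports how many nerves meet one wording and not the other.

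**The case for a change.** The strongest case for a change is that the defect lies in what the Protocol states, not in a detail left for later. The definition sits inside the first objective, the gloss equates two descriptions that are not identical, and no precedence is given. The bibliography lists no source for the named classification itself. The planning study is described as one in which "200 optic nerve canals were assessed and grouped into four types based on the modification of" that classification, and the rules of the modification are not given. A clarification before the September categorisation would cost almost nothing, whereas an unclear open entry might later require scans to be read again.

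What stands is that the sentences differ, that no tie-break is written and that exactly 50% has no home. What does not stand is the step from there to an undefined result. The text equates Type 4 with the Onodi cell and says what that cell is, which settles the ethmoid-only nerve and points to Type 4 where descriptions overlap. The open entry is a matter of form layout, since the definitions are in the Protocol to which the form is attached. The 50% boundary is a single point on a continuous judgement and does not touch Type 4.

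**Conclusion.** The concern does not call for a change. It is a loose wording that radiologists applying a named four-type classification would fill sensibly: one type per nerve, with an Onodi configuration coded as Type 4. Tidying the sentence or printing the codes 1 to 4 on the form would do no harm, but the analysis does not depend on it, and a sensitivity analysis under the alternative wording would be out of proportion for a descriptive review of scans.

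The effect on the Type 4 prevalence cannot be determined from the documents in either size or direction, and no wrong result is shown. The sample size of 637 canals and 319 scans is unaffected. The conclusion assumes that readers take the bracketed gloss at its word and apply one rule throughout.

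### Halving 637 canals to 319 patients treats a patient's two canals as independent; at a right-left correlation of about 0.4, the 99% margin at 60% is about ±5.9 points, not ±5

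*Protocol*

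**What the plan says.** Section 4.C (Sample size) of the Protocol uses n = Z²P(1−P)/d². Its inputs are "Z- 2.576 (for 99 percent confidence interval"), a prevalence of 60% for the commonest variant, taken from an earlier study, and a margin of error of 5%. The result is 637 canals. The protocol then moves from canals to patients: "Since 1 patient has 2 optic nerve canals, number of CT to be studied =319". The requirement is given as "Minimum 319 patient's CT scan". No within-patient correlation or design effect is mentioned.

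Section 3 (Literature Review) describes a study in Karnataka and lists how often each of the four types occurred, in ascending order of type; the sentence ends: "Type 4 optic nerves was present in 83.33%, 8.87%, 12.1%, and 21.78% respectively". It then turns to findings on both sides. For the commonest type it reports: "Bilateral Type 1 optic nerves was present in 58.88% patients". The second and third types each have a bilateral figure of 3.23%. The entry for the remaining type reads: "bilateral Type 4 optic nerve was seen in 10 (8.06%) cases". A later sentence in the same paragraph gives Type 1 as 83.88% instead of 83.33%.

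**The concern.** The formula holds for independent observations. Two canals in the same head share anatomy, and if they tend to be of the same type, 638 canals from 319 patients carry less information than 638 unrelated canals. The calculation has no slack: with zero correlation the margin is exactly ±5.00 points, so any positive correlation pushes it beyond ±5 at a prevalence of 60%.

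A margin of ±5 points at 99% confidence is the only precision the protocol states, and it is the sole basis for 319. If it is not met at the stated minimum, the justification of the sample size is wrong as written.

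**Working it through.** **1. The plan's own figure.** 2.576² × 0.6 × 0.4 / 0.05² = 637.03. Half of this, rounded up, is 319. Both figures reproduce, so the arithmetic is correct and the question is the conversion.

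**2. What the Karnataka percentages measure.** 83.33 + 8.87 + 12.1 + 21.78 = 126.08%, so they cannot be shares of nerves. Ten cases at 8.06% imply 10/0.0806 ≈ 124 patients. Reading the four percentages as patients with the type on at least one side gives these counts out of 124:

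| | Type 1 | Type 2 | Type 3 | Type 4 | Sum |
|---|---|---|---|---|---|
| At least one side | 104 | 11 | 15 | 27 | 157 |
| Both sides | 73 | 4 | 4 | 10 | 91 |

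157 + 91 = 248, exactly two nerves for each of 124 patients. This closure uses the 83.88% figure for Type 1 (104/124 = 83.87%). The 83.33% figure matches no whole count (103/124 = 83.06%), and with it the percentages sum to 199.48% instead of 200.03%.

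**3. Implied correlation.** With a = share with the type on at least one side and b = share with it on both sides, the per-nerve share is p = (a + b)/2 and the correlation is r = (b − p²)/(p(1 − p)).

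- Type 1 with 83.88%: p = 0.7138, r = (0.5888 − 0.7138²)/(0.7138 × 0.2862) = 0.388. With 83.33%: p = 0.711, r = 0.405.
- Type 2: r = 0.50. Type 3: r = 0.37. Type 4: r = 0.46.

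Independence would predict 0.7138² ≈ 51% of patients with bilateral Type 1, against 58.88% quoted, and 0.1492² ≈ 2.2% with bilateral Type 4, against 8.06% quoted. Resampling the Type 1 counts (73 both sides, 31 one side, 20 neither; 200,000 replicates) gives a 95% range for r of 0.20 to 0.56.

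**4. Margin at the minimum sample.** With two canals per patient the design effect is 1 + r, so the half-width is z × √(P(1 − P)(1 + r)/638). At P = 0.60:

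| r | 99% half-width (points) | 95% half-width (points) | Confidence carried by ±5 | Patients for ±5 at 99% |
|---|---|---|---|---|
| 0 | 5.00 | 3.80 | 99.0% | 319 |
| 0.2 | 5.47 | 4.16 | 98.1% | 383 |
| 0.4 | 5.91 | 4.50 | 97.1% | 446 |
| 0.56 | 6.24 | 4.75 | 96.1% | 497 |

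At r = 0.4 the 638 canals are worth 638/1.4 ≈ 456 independent ones. The last column is 637.03 × (1 + r)/2, rounded up. Simulating 319 patients (200,000 replicates) gave 99.0, 98.2, 97.1 and 96.3% of estimates within ±5 points, in line with the formula.

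**5. Other prevalences.** At r = 0.4 the 99% margin exceeds ±5 for any per-canal prevalence between about 22% and 78% (28% to 72% at r = 0.2; 19% to 81% at r = 0.56). Type 2 at 26.85%, the highest Type 2 figure in the literature review, gives ±5.35 at r = 0.4 and 4.52 × √1.5 = ±5.54 at the Type 2 correlation of 0.50. Prevalences of 11% to 17.5% stay within ±5 over the range considered (±3.8 to ±4.6 at r = 0.4; ±4.0 to ±4.8 at r = 0.56).

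**The case against.** The protocol states no correlation. The value of 0.4 comes from one study of about 124 patients and depends on reading its percentages as at least one side. The 60% used for sizing comes from a different study, quoted without bilateral counts. The range 0.20 to 0.56 reflects sampling error in the Type 1 counts only; it does not cover doubt about the reading or about transfer to this hospital. All of this stands, and it makes the size of the shortfall conditional. It does not change the direction: the counts close exactly at 248 nerves, all four types give a positive correlation, and both Type 1 figures give about 0.4.

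No bilateral data are quoted for dehiscence or for clinoid pneumatization, so applying a Type 1 correlation to them is a further assumption. At 17.5% the 99% margin would pass ±5 only if r exceeded about 0.66, and at 15% only if r exceeded about 0.89.

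The practical stakes are low. The study is descriptive, nothing hinges on ±5 points, and 319 is a minimum: section 4.D includes all eligible scans and states no cap. At 95% confidence the same sample stays within ±5 at P = 60% up to r of about 0.73. This limits the severity, but section 4.C still presents 319 as enough for ±5 at 99%. An analysis that allows for pairing would give a valid interval but would not make it narrower.

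**Conclusion.** The concern holds, as a minor one. Section 4.C reaches 319 patients only by assuming that a patient's two canals are uncorrelated, and the protocol's own literature review points to a positive correlation. At r = 0.4 the margin at the minimum sample is about 0.9 points wider than stated (0.5 to 1.2 points over r = 0.2 to 0.56). This rests on three assumptions: the at-least-one-side reading of the Karnataka figures, transfer of that correlation to this hospital's patients, and per-canal prevalence as the target, which is the unit the protocol sizes in. That the margin is wider than stated is well supported; by how much is less certain. The prevalence estimates are not biased, and only the planning statement is affected.

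**What to change.** Keep the minimum of 319 patients and replace the claim of ±5% at 99% confidence in section 4.C with wording such as:

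> Minimum 319 patients (638 canals). Allowing for a within-patient correlation of about 0.4 (range 0.2 to 0.56), inferred from the cited Karnataka data and assumed to apply to our patients, the expected margin at this minimum for a per-canal prevalence of 60% is about ±5.9 percentage points at 99% confidence (range ±5.5 to ±6.2), or about ±4.5 at 95% (±4.2 to ±4.7).

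The cost is one rewritten paragraph, a less favourable stated precision and no extra scans. If the investigators prefer to keep ±5 points at 99%, the same assumptions call for about 446 patients (383 to 497).
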